4.5 Prior IBS-D Symptom Management Questionnaire

The number and percentage of patient's taking each category of medication (Loperamide, Antidiarrheals (other than loperamide), Antidepressants, Anticholinergics/Antispasmodics) will be summarized with p-values for testing differences between treatment groups. Furthermore, the responses to follow-up questions will be summarized by each category of medication and by questions.

Further text answers will be provided in a listing.

5. Duration to Study Treatment(s) and Compliance of Treatment

Duration of treatment is defined as: [(last dose date - first dose date) + 1].

The duration of treatment will be summarized by descriptive statistics. A listing will present the first dose date and the last dose date, the dates and days of interruption, and the overall days of exposure.

The total dose for a patient is defined as the sum of the patient reported dose on each day with dosing information (i.e., without any imputation) during 12-week treatment period. The total dose will be summarized by descriptive statistics.

Study drug compliance will be calculated as the number of tablets taken divided by the target number of tablets to be taken during 12-week treatment period.

$$\text{Overall Compliance (\%)} = \frac{(\text{Number of tablets taken}) \times 100 \%}{\text{Target number of tablets to be taken}}$$

The target number of tablets to be taken is calculated as: (last dose date – first dose date + 1) x 2, since the dose is 1 tablet BID. The number of tablets taken is obtained by: (no. dispensed – no. returned).

[figure not shown]
If the drug is not returned at one visit for a patient, the compliance for the patient will be set to missing and the patient will be excluded from the analysis.

[figure not shown]
Treatment compliance will be summarized by descriptive statistics and also as frequency counts and percentages for the following categories (<80 % vs ≥80%).

The diary entry compliance will be summarized by compliance days categories (< 60 days vs ≥ 60 days) during the 12-week treatment period (84 days). For partial diary entry, the diary entry compliance is defined as if a patient's diary entry has EITHER WAP score and BSS score OR WAP score and bowel movement frequency data for a day, this patient will be considered as diary entry compliance for the day.

A listing will be provided for drug administration data, including number of tablets dispensed, returned, and the number not returned also not taken, etc.

6. Efficacy Analyses

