### 5.4 Management of Clinical Supplies

#### 5.4.1 Study Drug Packaging and Storage

The study drug will be packaged and labeled according to current Good Manufacturing Practices and local regulations.

The study drug will be packaged in child-resistant 70-count bottles by [REDACTED] on behalf of the sponsor. The bottles will be labeled with double-blinded labels.

Each bottle will contain a (randomized) dosage for 1 patient for 4 weeks of the 12-week double-blind treatment period and will be distributed at each of the scheduled visits during the treatment period: randomization (visit 3), week 4 (visit 4), and week 8 (visit 5).

Recommended storage conditions for study drug are as per the commercial product. The study drug will be stored in controlled temperatures ranging from [REDACTED]

[REDACTED]

[REDACTED] The storage conditions will be indicated on the label. Expiry dates will

be provided directly on the label or communicated to the sites with an expiry memo and/or managed electronically if drug distribution for the study is managed by IxRS.

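### The SAP's compliance formula counts tablets recorded as neither returned nor taken as if they had been taken, and its denominator does not match its 12-week wording

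*SAP*

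**What the plan says.** All the compliance rules are in SAP section 5.

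- Numerator: "The number of tablets taken is obtained by: (no. dispensed – no. returned"). Nothing else is subtracted.
- Denominator in words: "target number of tablets to be taken during 12-week treatment period".
- Denominator as a formula: "last dose date – first dose date + 1) x 2".
- Unreturned drug: "If the drug is not returned at one visit for a patient, the compliance for the patient will be set to missing", and the patient leaves the compliance analysis.
- Reporting: descriptive statistics, plus counts of patients below 80% and at or above 80%.
- Listing, at the end of the section: tablets dispensed, tablets returned, and "the number not returned also not taken".

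On supply, Protocol section 5.4.1 specifies "child-resistant 70-count bottles". Protocol section 5.3 provides one bottle at each of visits 3, 4 and 5, with 1 tablet taken twice daily.

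**The concern.** The plan expects to hold a count of tablets that did not come back and were not swallowed, yet its formula treats every tablet that did not come back as swallowed. The listing and the formula therefore contradict each other for any patient in whom that count is above zero. The error has one direction: it can only raise the reported percentage.

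The second problem is one of naming. A reader of the compliance table would take the words to mean a share of the full 12-week supply need, whereas the formula gives a share of the patient's own dosing span.

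At stake is how well the table describes adherence, and in particular how many patients it places at or above 80%.

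**Working it through.** The documents state no expected compliance figure, so there is none to reproduce. The check applies the SAP formula directly.

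**Inputs**
- Treatment period: 84 days (SAP section 5). Tablets per day: 2 (Protocol section 5.3).
- Dispensed: 3 bottles × 70 = 210 (Protocol sections 5.3 and 5.4.1).
- Needed over 84 days: 84 × 2 = 168. Spare: 210 − 168 = 42, or 14 per bottle.
- Tablets taken, returned and lost per patient: assumptions, since the documents give no frequency of lost tablets.

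**Numerator**

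Write D for dispensed, R for returned, L for neither returned nor taken, and T for taken, so that D = T + R + L. The SAP numerator is D − R = T + L. Over an 84-day span the reported value is 100 × (T + L)/168, so it exceeds the true value by 100 × L/168. That is about 0.6 points per lost tablet, 8.3 points for 14 tablets (14/168) and 25.0 points for 42 (42/168).

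For a patient who takes 100 tablets, with the loss varied:

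| Taken | Lost | Returned | SAP formula | Lost tablets subtracted |
|---|---|---|---|---|
| 100 | 0 | 110 | 100/168 = 59.5% | 59.5% |
| 100 | 14 | 96 | 114/168 = 67.9% | 59.5% |
| 100 | 28 | 82 | 128/168 = 76.2% | 59.5% |
| 100 | 35 | 75 | 135/168 = 80.4% | 59.5% |
| 100 | 42 | 68 | 142/168 = 84.5% | 59.5% |

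The 80% line is 0.80 × 168 = 134.4, so 135 tablets. With 210 dispensed, anyone who returns 75 or fewer over an 84-day span is classed at or above 80%, however many of the remaining tablets were swallowed. A patient with T below 135 is misclassified once L reaches 135 − T. That takes 35 lost tablets when T = 100, 15 when T = 120, and 1 when T = 134 (135/168 = 80.4% against 134/168 = 79.8%).

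**Does the missing-return rule catch this?** It applies when drug is not returned at a visit. It says nothing about a bottle that comes back with some tablets unaccounted for, which is the case above.

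**Denominator**

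The formula gives 2 × span, and the wording suggests 168. They are equal only when the span is 84 days. For patients who take every dose until they stop:

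| Last dose | SAP formula | Against 168 |
|---|---|---|
| Day 28 | 56/56 = 100% | 56/168 = 33.3% |
| Day 56 | 112/112 = 100% | 112/168 = 66.7% |
| Day 67 | 134/134 = 100% | 134/168 = 79.8% |
| Day 84 | 168/168 = 100% | 168/168 = 100% |

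**The case against.** **The denominator is a recognised convention.** A first-to-last-dose denominator is ordinary on-treatment compliance, the SAP states its formula explicitly, and the 12-week phrase may simply name the window. A patient who takes every dose for 28 days and then withdraws was compliant while treated. Early stopping is also visible elsewhere: disposition with reasons and a listing of premature discontinuations (SAP section 3.2), and treatment duration and total patient-reported dose (SAP section 5). This stands. What remains is a mismatch between words and formula, which a label resolves.

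**Not every rule inflates compliance.** A reader might infer that the numerator, the denominator and the missing-return rule all push the figure upward. The documents do not support that. Interruption days stay in the denominator, which lowers the ratio for patients who pause and resume. The missing-return rule prevents one form of inflation: a wholly unreturned bottle over 28 days would otherwise score 70/56 = 125%. That the patients it removes are poorer adherers is plausible, but nothing in the documents establishes it.

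**The example is constructed.** It needs a patient who loses 42 tablets from bottles that were otherwise returned. That is true, and no frequency can be given. It shows that misclassification is possible, not that it is common.

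**Losses are not hidden.** They are listed, and Protocol section 5.5.2 treats losing medication as an error to be documented. This is also true, but the summary table and its 80% split would still contradict the listing.

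**Conclusion.** The numerator omits a count that the plan itself lists, so compliance is overstated for every patient in whom that count is above zero, by about 0.6 points per tablet over an 84-day span. On the illustrative counts the gap is 84.5% against 59.5%, enough to cross the 80% cut. The mechanism follows from the SAP text; its frequency is unknown. The denominator needs an accurate name, because its wording and its formula agree only for an 84-day span.

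The consequence is confined to a descriptive summary. The analysis sets defined are ITT and Safety only (SAP section 2.1), and neither the chi-square test nor the supportive logistic model uses compliance (SAP sections 6.3.1 and 6.3.2). A reader might go further and say that the compliance table is the plan's basis for judging whether a null result reflects poor adherence. No text shown gives it that role, and the same rules apply to both arms, so no between-arm distortion follows from them.

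**What to change.** In SAP section 5:

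1. Define tablets taken as dispensed minus returned minus the listed count of tablets neither returned nor taken.
2. Label the ratio *compliance while on treatment* and reword the denominator to match its formula. Optionally, show a second ratio against 168 tablets beside it.
3. Keep the rule that sets compliance to missing when drug is not returned at a visit, and report per arm how many patients it removes. Scoring such patients only on the intervals with returned bottles is not advised: if adherence was worst in the unreturned interval, they would be judged on their better ones.

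The cost is a change of wording and minor programming on fields the plan already lists. No new data are needed and the primary analysis does not change. Reported compliance becomes slightly less favourable.

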### **5.5.2 Medication Errors**

Dispensing study treatment to be taken by patients in an outpatient study increases risk for medication errors. All errors in medication dispensing or administration must be carefully documented. These errors may include but are not limited to providing the wrong dose, losing medication, or administration at the wrong time of day. Medication adherence will be emphasized at every study visit. Additional adherence procedures and/or technology, such as a mobile device application, may be implemented.

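### The SAP compliance formula counts lost tablets as taken, although a count of tablets neither returned nor taken is planned for listing (minor; descriptive summary only)

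*SAP*

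**What the plan says.** SAP 5 defines overall compliance as tablets taken divided by target tablets, times 100.

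- Numerator: "The number of tablets taken is obtained by: (no. dispensed – no. returned".
- Denominator: "The target number of tablets to be taken is calculated as: (last dose date – first dose date + 1) x 2, since the dose is 1", that is, two per day of treatment.
- Missing data: "If the drug is not returned at one visit for a patient, the compliance for the patient will be set to missing"; such patients are left out of the compliance analysis.
- Reporting: compliance is "summarized by descriptive statistics and also as frequency counts and percentages for the following categories (<80 % vs ≥80" percent).
- Listing: the drug administration listing is described as "including number of tablets dispensed, returned, and the number not returned also not taken, etc".

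Protocol 5.7 says only that sites assess compliance by pill count and gives no formula. Protocol 5.5.2 requires errors in dispensing or administration to be documented and gives examples: "These errors may include but are not limited to providing the wrong dose, losing medication, or administration at the wrong time of day". On supply, Protocol 5.4.1 states "The study drug will be packaged in child-resistant 70-count bottles", with one bottle handed out at each of visits 3, 4 and 5.

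**The concern.** A dispensed tablet can end in one of three ways: returned, taken, or neither. The SAP recognises all three in its listing but only two in its formula. Subtracting returned from dispensed leaves the taken tablets plus those neither returned nor taken, and the SAP labels the whole remainder as taken.

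A lost tablet can therefore raise reported compliance and can never lower it, so the error does not average out across patients. What is at stake is the accuracy of the compliance summary and of the table split at 80%. A patient below the cut can be shown above it because tablets went missing.

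**Working it through.** The plan states no compliance result, so there is no figure of its own to reproduce. The check compares the SAP formula with one that removes the third count.

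**Inputs**
- Treatment period: 84 days (SAP 5).
- Target over a full course: 84 × 2 = 168 tablets (SAP 5 denominator).
- Dispensed over a full course: 3 bottles × 70 = 210 tablets (Protocol 5.4.1), which is 210 − 168 = 42 more than the target, or 14 per bottle.
- Tablets lost per patient: not given in the documents; the values below are assumptions.

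**Formulas**, with D dispensed, R returned, L neither returned nor taken, T target:
- SAP: 100 × (D − R) / T
- Corrected: 100 × (D − R − L) / T
- Overstatement: 100 × L / T

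**Per lost tablet**
- 84 days: 100 / 168 = 0.60 points.
- 28 days: T = 28 × 2 = 56, so 100 / 56 = 1.79 points.

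**Single patients over 84 days** (D = 210, T = 168)

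| Taken | Lost | Returned | SAP formula | Corrected |
|---|---|---|---|---|
| 126 | 9 | 75 | 135/168 = 80.4% | 126/168 = 75.0% |
| 134 | 5 | 71 | 139/168 = 82.7% | 134/168 = 79.8% |
| 126 | 14 | 70 | 140/168 = 83.3% | 126/168 = 75.0% |
| 168 | 14 | 28 | 182/168 = 108.3% | 168/168 = 100.0% |

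The 80% cut is 0.80 × 168 = 134.4, so 135 tablets are needed to reach it. The first three patients are below it and are reported above it. The last took every dose, and the lost spare tablets alone push the figure past 100%.

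**Mean effect under an assumed loss rate.** If a share s of patients each lose 14 tablets, the mean rises by s × 100 × 14/168 = s × 8.33 points:
- s = 2%: 0.17 points
- s = 5%: 0.42 points
- s = 10%: 0.83 points

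Fourteen is the surplus in one bottle (70 − 56). Nothing in the documents says that patients lose that many.

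**The case against.** The strongest case on the other side is that nothing inferential rests on this number. Efficacy is analysed in all randomised patients and safety in all who took at least one dose (SAP 2.1). The visible text defines no per-protocol set, no efficacy analysis by compliance and no test on the compliance table. This stands, and it makes the point a minor one. A reader might infer that the formula weakens the efficacy conclusion; the documents do not support that.

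Three further arguments stand in whole or in part.

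- **Other exposure data.** A reader might take the compliance table as the trial's only evidence of how much drug was taken. It is not. SAP 5 also summarises total dose from patient-reported daily dosing, which does not use the pill count, and lists interruptions and days of exposure.
- **The listing.** A reader might infer that the summary would contradict the listing. The listing as described holds raw counts. The visible text promises no listed compliance percentage, so there is no second figure to conflict with, and a reader could make the adjustment by hand. That mitigates the error but does not correct the reported table.
- **The missing-data rule.** On its natural reading the rule removes patients who return no drug at a visit, which takes out the largest losses. The wording is loose: it does not say whether a partly depleted return or an empty bottle counts as not returned. Read so widely that any lost tablet triggers it, the rule would exclude patients whose intake could be calculated. Either reading needs a clarifying sentence.

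It is also fair to say that a site cannot count a tablet that is neither returned nor taken, so the third count may depend on what the patient says. The documents do not describe how it is obtained.

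**Conclusion.** The formula is wrong as written, because it treats as taken a group of tablets that the same SAP section separately identifies as not taken. The direction is certain: upward, by 0.60 points per lost tablet over 84 days and 1.79 over 28 days. Misclassification at the 80% cut is possible for patients a little below it, and how far below depends on how many tablets were lost.

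The overall size is not known. It depends on how many patients have a partial loss and how large that loss is, and the documents give neither. The range of 0.17 to 0.83 points in the mean holds only if 2% to 10% of patients lose 14 tablets each. The conclusion also assumes that the set-to-missing rule applies to a visit with no return and not to a partial loss.

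This is a minor correction to a descriptive summary. The primary chi-square test, its power, the sample size of 340 and the ITT efficacy results are unaffected.

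**What to change.** In SAP 5, define:

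number of tablets taken = no. dispensed − no. returned − no. not returned and not taken

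Use this count for overall compliance and for the table split at 80%. Add a sentence saying that compliance is set to missing when no drug is returned at a visit, or when the neither-returned-nor-taken count is unknown, and state whether an empty bottle counts as a return.

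The cost is one term in a formula and one or two sentences, using a count already planned for the drug administration listing. Sample size and primary analysis do not change. There are two drawbacks: the added count may rest on patient report, and reported compliance may be slightly lower. Some patients may also move to missing if the count was not recorded.

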6.3 Primary Efficacy Analyses

The primary efficacy endpoint is the proportion of primary composite responders determined over the 12-week double-blind treatment period. A primary composite responder is defined as a patient who meets the daily composite response criteria for at least 50% of days with diary entry during the interval of week 1-12.

A patient must meet BOTH of the following criteria on a given day to be a daily composite responder:

- Daily pain response: WAP score in the past 24 hours improved by $\geq 40\%$ compared to baseline pain (average of daily WAP in the week prior to randomization).

- Daily stool consistency response: BSS score <5 (i.e., score of 1, 2, 3, or 4); or the absence of a bowel movement if accompanied by $\geq 40\%$ improvement in WAP compared to baseline pain.

To be eligible to be a primary composite responder, a patient must have a minimum of 60 days of diary entries, including partial entries, over the interval of week 1-12. A partial diary entry should consist of EITHER WAP score and BSS score OR WAP score and bowel movement frequency equals 0 to determine whether a patient is a daily responder. Any patient with fewer than 60 days of diary entry will be considered as a non-responder.

6.3.1 Primary Analyses for Primary Efficacy Endpoint

The primary analysis is to evaluate the proportions of primary composite responders between the eluxadoline and placebo groups. These 2 proportions are represented as $\pi_{\text{Eluxadoline}}$ and π_{Placebo} . The primary hypotheses for this study are described below:

$$H_0: \pi_{\text{Eluxadoline}} - \pi_{\text{Placebo}} = 0$$

vs

$$H_A: \pi_{\text{Eluxadoline}} - \pi_{\text{Placebo}} \neq 0$$

The number and the percentage of responders and non-responders will be summarized in a table with p-value from chi-square test to test the different response rates between treatment groups.

6.3.2 Other Analysis for Primary Efficacy Endpoint

As a supportive analysis, the primary endpoint will also be analyzed using logistic regression model with treatment group, the baseline pain score, and the baseline stool consistency score as exploratory variables.

[figure not shown]
6.4 Secondary Efficacy Analyses

[figure not shown]
The following are the secondary efficacy endpoints:

- Proportion of stool consistency responders: defined as patients who meet the daily stool consistency response criteria (BSS <5, or absence of a bowel movement) for $\geq 50\%$ of days with diary entries over a certain time period. This endpoint is defined for the 12-week treatment period and for each 4-week interval (week 1 to 4, 5 to 8, and 9 to 12). For the 12-week treatment period, the $\geq 50\%$ requirement is the same as specified for the primary efficacy endpoint in Section 6.3. For each of the 4-week intervals, a responder must have a minimum of 20 days of diary entries over the 4 weeks. Any patient with fewer than 60 days (for 12-week period) or with fewer than 20 days (for 4-week interval) of diary entries will be considered as a non-responder.

- Proportion of pain responders: defined as patients who meet the daily pain response criteria (as defined in Section 6.3) for $\geq 50\%$ of days with diary entries over a certain time period. This endpoint is defined for the 12-week treatment period and for each 4-week interval (week 1 to 4, 5 to 8, and 9 to 12). For the 12-week treatment period, the $\geq 50\%$ requirement is the same as specified for the primary efficacy endpoint in Section 6.3. For each of the 4-week intervals, a responder must have a minimum of 20 days of diary entries over the 4 weeks. Any patient with fewer than 60 days (for 12-week period) or with fewer than 20 days (for 4-week interval) of diary entries will be considered as a non-responder.
- Proportion of monthly composite responders: defined as patients who meet the daily composite response criteria (as defined in Section 6.3) for at least 50% of days with diary entry for each 4-week interval (week 1 to 4, 5 to 8, and 9 to 12). For each of the 4-week intervals, a responder must have a minimum of 20 days of diary entries over the 4 weeks. Any patient with fewer than 20 days of diary entries for the 4-week interval will be considered as a non-responder.

The secondary endpoints will be analyzed by the number and percentage of the corresponding responders with p-value from chi-square test to test the different response rates between treatment groups. No adjustment for the multiplicity of the endpoints will be performed.

[figure not shown]

[figure not shown]
8. Interim Analyses

[figure not shown]
There will be no interim analysis for this study.

9. Deviations from Protocol

[figure not shown]
This analysis mentioned in protocol section [7.7.3](#), “The mixed-effect model for repeated measures method will be used to analyze these endpoints with treatment group as the factor and baseline endpoint values as covariate.” is not performed.

